#### **10.1.2.2. Laboratory data**

Missing laboratory results (including immunological data) will not be replaced.

#### **10.1.2.3. Daily recording of solicited symptoms**

##### ***10.1.2.3.1. Studies with paper diaries***

Denominators for the summary of local (or general) solicited symptoms will be calculated using the number of subjects who respond “Yes” or “No” to the question concerning the occurrence of local (or general) symptoms.

When a specific symptom is marked as having not occurred following a specific vaccination (i.e. SDTM CE.CEOCCUR=N for the specified post-vaccination period for the symptom in question), all daily measurements will be imputed as Grade 0.

When a specific symptom is marked as having occurred following a specific vaccination (i.e. SDTM CE.CEOCCUR=Y for the specified post-vaccination period for the symptom in question), any missing daily recordings will be given imputed values to allow them to contribute to the ‘Any’ rows but not to specific grade rows of the symptom summary tables.

When the occurrence of a specific symptom is not present (i.e. SDTM CE.CEOCCUR is neither Y nor N for the specified post-vaccination period for the symptom in question) but the group of symptoms (local or general) is marked as having occurred (i.e. SDTM CE.CEOCCUR=Y), all missing daily recordings will be given imputed values to allow them to contribute to the ‘Any’ rows but not to specific grade rows of the symptom summary tables.

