12.5.8. Detecting and recording adverse events, serious adverse events and pregnancies

A pDiary, hereafter referred to as Subject Diary will be used in this study to capture solicited and unsolicited adverse events. The subject should be trained on how and when to complete each field of the Subject Diary.

The subjects will be instructed to contact the investigator immediately should the subjects manifest any signs or symptoms they perceive as serious.

Subject Diary training should be directed at the individual(s) who will perform the measurements of adverse events and who will enter the information into the Subject Diary. This individual may not be the subject, but if a person other than the subject enters information into the Subject Diary, this person's identity must be documented in the Subject Diary. Any individual that makes entries into the Subject Diary must receive training on completion of the Subject Diary at the time of the visit when Subject Diary is dispensed. This training must be documented in the subject's source record.

CONFIDENTIAL209538 (NTHI MCAT-009)
Protocol Amendment 1 Final

At each NTHi-Mcat vaccination visit, diary cards will be provided to the subject. The subject will be instructed to measure and record the axillary body temperature, and any solicited local/general AEs (i.e. on the day of vaccination and during the next 6 days) or any unsolicited AEs (i.e. on the day of vaccination and during the next 29 days occurring after vaccination. The subject will be instructed to return the completed diary card to the investigator at the next study visit.

- Collect and verify completed diary cards during discussion with the subject on Day 121; Day 181; Day 271 (Visit 4_1, Visit 4_3, Visit 4_6), and Day 181; Day 241; Day 331 (Visit 6_1, Visit 6_3, Visit 6_6) in the Sh_NTHi-Mcat groups and on Day 31 (Visit 2) and Day 91 (Visit 4) in the NTHi-Mcat group.
- Any unreturned diary cards will be sought from the subject through telephone call(s) or any other convenient procedure.

The investigator will transcribe the collected information into the eCRF in English.

12.5.8.1. Time period for detecting and recording adverse events, serious adverse events and pregnancies

All AEs during 30 days following administration of each dose of NTHi-Mcat study vaccine (Day 1 to Day 30) must be recorded onto/into the appropriate section of the eCRF, irrespective of intensity or whether or not they are considered vaccination-related.

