12.5.8.2.2. Assessment of adverse events**1. Assessment of intensity**

The intensity of the following solicited AEs will be assessed as described:

CONFIDENTIAL209538 (NTHI MCAT-009)
Protocol Amendment 1 Final**Table 24 Intensity scales for solicited symptoms**

Adverse Event	Intensity grade	Parameter
Pain at injection site	0	None
	1	Mild: Any pain neither interfering with nor preventing normal every day activities.
	2	Moderate: Painful when limb is moved and interferes with every day activities.
	3	Severe: Significant pain at rest. Prevents normal every day activities.
Redness at injection site		Record greatest surface diameter in mm
Swelling at injection site		Record greatest surface diameter in mm
Temperature*		Record temperature in °C (with 1 decimal)
Headache	0	Normal
	1	Mild: Headache that is easily tolerated
	2	Moderate: Headache that interferes with normal activity
	3	Severe: Headache that prevents normal activity
Fatigue	0	Normal
	1	Mild: Fatigue that is easily tolerated
	2	Moderate: Fatigue that interferes with normal activity
	3	Severe: Fatigue that prevents normal activity
Gastrointestinal symptoms (nausea, vomiting, diarrhoea and/or abdominal pain)	0	Normal
	1	Mild: Gastrointestinal symptoms that are easily tolerated
	2	Moderate: Gastrointestinal symptoms that interfere with normal activity
	3	Severe: Gastrointestinal symptoms that prevent normal activity
Myalgia	0	Normal
	1	Mild: Myalgia that is easily tolerated
	2	Moderate: Myalgia that interferes with normal activity
	3	Severe: Myalgia that prevents normal activity
Chills	0	Normal
	1	Mild: Chills that are easily tolerated
	2	Moderate: Chills that interfere with normal activity
	3	Severe: Chills that prevent normal activity

*Fever is defined as temperature $\geq 37.5^{\circ}\text{C}$. The preferred location for measuring temperature in this study will be the axilla

The maximum intensity of local injection site redness/swelling will be scored at GSK Biologicals as follows:

- 0: < 20 mm diameter
- 1: ≥ 20 mm to ≤ 50 mm diameter
- 2: > 50 mm to ≤ 100 mm diameter
- 3: > 100 mm diameter

Temperature will be scored at GSK Biologicals as follows:

- 0: $< 37.5^{\circ}\text{C}$
- 1: 37.5°C to 37.9°C
- 2: 38.0°C to 38.9°C
- 3: $\geq 39.0^{\circ}\text{C}$

CONFIDENTIAL209538 (NTHI MCAT-009)
Protocol Amendment 1 Final

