**5.4.2. Additional considerations****5.4.2.1. Analysis of solicited AEs**

The analysis of solicited AEs will be performed on the Solicited safety set.

The maximum intensity of local injection site redness/swelling will be scored at GSK Biologicals as follows:

Grade 0: <20 mm diameter

Grade 1: ≥20 mm to ≤50 mm diameter

Grade 2: >50 mm to ≤100 mm diameter

Grade 3: >100 mm diameter

**CONFIDENTIAL**209538 (NTHI MCAT-009)  
Statistical Analysis Plan Amendment 2

Temperature (i.e. fever) will be scored at GSK Biologicals as follows:

- Grade 0:  $<37.5^{\circ}\text{C}$
- Grade 1:  $37.5^{\circ}\text{C}$  to  $37.9^{\circ}\text{C}$
- Grade 2:  $38.0^{\circ}\text{C}$  to  $38.9^{\circ}\text{C}$
- Grade 3:  $\geq39.0^{\circ}\text{C}$

Fever, defined as a body temperature of  $\geq37.5^{\circ}\text{C}$  irrespective of route of measurement, will be integrated to the summaries as a general AE.

In addition, body temperature will be broken down into  $0.5^{\circ}\text{C}$  increments:

- $<36.0$
- $36.0 - 36.4$
- $36.5 - 36.9$
- $37.0 - 37.4$
- $37.5 - 37.9$
- $38.0 - 38.4$
- $38.5 - 38.9$
- $39.0 - 39.4$
- $39.5 - 39.9$
- $\geq40.0$

Compliance of subjects in completing solicited AEs information will be reported as the percentage of subjects completing at least 80% of the diary entries related to local and general solicited AEs.

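### The SAP rule for a solicited symptom marked 'No' is not limited to missing days; read literally, it would reset recorded fever, redness or swelling to Grade 0

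*SAP*

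**What the plan says.** SAP 10.1.2.3.1 (paper diaries) gives three rules for daily solicited data, according to how the symptom is marked.

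- **Marked 'No'.** The rule opens "When a specific symptom is marked as having not occurred following a specific vaccination", with CEOCCUR=N as the trigger, and ends "all daily measurements will be imputed as Grade 0".
- **Marked 'Yes'.** Here "any missing daily recordings will be given imputed values", so that the subject counts in the 'Any' row but in no specific grade row.
- **Symptom unmarked, symptom group marked 'Yes'.** Here "all missing daily recordings will be given imputed values", with the same effect.

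The numerator table in the same section counts a subject in the 'At least Grade 1' row on the strength of a single day at Grade 1, 2 or 3. It sets no condition on the Yes/No mark.

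SAP 5.4.2.1 defines fever as a body temperature of 37.5 °C or more, which "irrespective of route of measurement, will be integrated to the summaries as a general AE". It grades redness and swelling from the diameter, with Grade 1 starting at 20 mm. Protocol 12.5.8.2.2 says the same of grading ("Temperature will be scored at GSK Biologicals as follows") and has the subject record diameters in millimetres. On collection, Protocol 12.5.8 says "The subject will be instructed to measure and record the axillary body temperature", and Protocol 12.5.3 places this in the evening. Neither section makes the measurement depend on feeling feverish.

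**The concern.** Of the three rules, only the 'No' rule omits the limit to missing values. A programmer who follows the text would write Grade 0 over whatever was recorded. For fever, redness and swelling, that lets the Yes/No mark override the measurement by which the SAP itself defines and grades the event. No rule says which source prevails, or that a query is raised, when the two disagree.

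The 'No' rule can remove events but cannot add them. All solicited reactions are treated as causally related (Protocol 12.5.8.2.2; SAP 5.4.2.3), so a lost event would also drop out of the related and combined tables and, where it applies, the Grade 3 tables. The fever row could also disagree with the 0.5 °C temperature table. That table has four bins below 37.5 °C, all of which are Grade 0, so it cannot be filled from grades alone and presumably uses the recorded temperatures. Reactogenicity of NTHi-Mcat after *Shingrix* is a secondary objective.

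**Working it through.** The plan states no figure on this point, so there is none to reproduce. The check compares the rules, applies two readings to one diary, and then sizes the effect on assumed inputs.

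**1. The passages side by side**

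| Source | What decides the grade when the symptom is marked 'No' and 38.2 °C is recorded | Result |
|---|---|---|
| SAP 10.1.2.3.1, 'No' rule read literally | The mark | Grade 0 |
| SAP 5.4.2.1, temperature grades | The temperature (38.0 to 38.9 °C) | Grade 2 |
| SAP 10.1.2.3.1, numerator table | Any day at Grade 1 to 3 | Counted as at least Grade 2 |

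**2. One invented seven-day diary, marked 'No'**

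| Day | 1 | 2 | 3 | 4 | 5 | 6 | 7 | Maximum |
|---|---|---|---|---|---|---|---|---|
| Temperature (°C) | 36.6 | 37.6 | 38.2 | missing | 36.8 | 36.7 | 36.5 | 38.2 |
| Literal rule | 0 | 0 | 0 | 0 | 0 | 0 | 0 | Grade 0 |
| Missing days only | 0 | 1 | 2 | 0 | 0 | 0 | 0 | Grade 2 |

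The readings differ only because days 2 and 3 reach 37.5 °C. Had every recorded value been below 37.5 °C, both would give Grade 0. The same holds for diameters below 20 mm.

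**3. Size on assumed inputs**

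Let *p* be the true share of subjects with the symptom at Grade 1 or higher, and *d* the share of those who are marked 'No'. Under the literal rule the reported rate is *p*(1 − *d*), so the shortfall is *p* × *d*. The documents give neither input; the values below are assumptions. The 135 is the planned number randomized per group (Protocol 7.2.2.2.1).

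| *p* | *d* | Shortfall (percentage points) | Subjects out of 135 |
|---|---|---|---|
| any | 0% | 0 | 0 |
| 10% | 1% | 0.1 | 0.14 |
| 10% | 5% | 0.5 | 0.68 |
| 10% | 10% | 1.0 | 1.35 |
| 30% | 1% | 0.3 | 0.41 |
| 30% | 5% | 1.5 | 2.03 |
| 30% | 10% | 3.0 | 4.05 |

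One affected subject moves a group's rate by 1/135 = 0.74 points. The actual denominator is the number who answered the Yes/No question (SAP 10.1.2.3.1). If that is below 135, the movement per subject is slightly larger.

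**The case against.** The strongest reply is that gap-filling was meant. The rule sits under SAP 10.1.2, which is about missing data, and it speaks of imputing. If the daily fields are left blank after a 'No', every day is missing and the wording is natural. The other two rules need the word 'missing' because in those cases some days may be filled and others blank. This is a fair account of the likely intention. It does not settle the matter: nothing says that recorded values are kept, the diary layout is not shown, and temperature is to be recorded regardless of symptoms.

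The second reply is that harm needs a self-contradictory record, and that several steps reduce these. Sites verify diaries in discussion with the subject, the investigator transcribes them (Protocol 12.5.8), and monitors verify source data (Protocol 12.4.8). This also stands. It makes contradictory records fewer, but it does not say what the analysis does with any that remain.

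Third, the rule is the same in all four groups, comparisons outside the primary objective are descriptive (SAP 6), and the neighbouring rules add subjects to the 'Any' row. These points limit the consequence. They do not reconcile the rule with the fever definition.

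A reader might also go further and infer that bias differs between groups. Table 3 allows remote contact at some diary-return visits of the 3- and 6-month groups (V6_3, V4_6, V6_6), and Protocol 8.1 lets diaries be mailed. Nothing in the documents shows that more contradictory entries survive there, so this remains only a possibility.

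**Conclusion.** The rule is wrong as written. Followed literally, it contradicts the measurement-based definition and grading in SAP 5.4.2.1 and the numerators in its own section. Whether any result would change depends on two things that the documents leave open: that the literal reading is programmed, and that records combining a 'No' mark with at least 37.5 °C or at least 20 mm remain after verification. If both hold, the bias is downward; if either fails, it is zero. The 0.1 to 3.0 points shown above rest wholly on the assumed 10% to 30% and 1% to 10%.

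Two stronger conclusions are tempting. One is that recorded events are in fact erased and reactogenicity is understated; no contradictory record is shown to exist, and the section's context favours gap-filling. The other is that conflict is routine because temperatures are recorded daily; a 'No' beside values below 37.5 °C is Grade 0 on either reading and loses nothing.

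Only the descriptive secondary reactogenicity tables are affected. The primary non-inferiority analysis is untouched.

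**What to change.** In SAP 10.1.2.3.1, insert 'missing' before 'daily measurements' in the rule for symptoms marked 'No'. Then add two statements:

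- For fever, redness and swelling, the grade is derived from the recorded temperature or diameter.
- A conflict between a 'No' mark and a recorded value at Grade 1 or higher is queried and, if unresolved, the recorded value is kept.

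The cost is one programming condition and possibly a few data queries. If gap-filling was always meant, the inserted word changes no result and only removes the ambiguity.

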**CONFIDENTIAL**

209538 (NTHI MCAT-009)  
 Statistical Analysis Plan Amendment 2

The following table shows how subjects contribute to each category for a specific solicited symptom over the Day X to Day Y post-vaccination period:

Solicited symptom category	Subjects included in the calculation of the numerator
Any	All subjects with at least one occurrence of the symptom at Grade 1, Grade 2, or Grade 3 between Day X and Day Y or with the symptom marked as present and at least one missing daily recording between Day X and Day Y
At least Grade 1	All subjects with at least one occurrence of the symptom at Grade 1, Grade 2, or Grade 3 between Day X and Day Y
At least Grade 2	All subjects with at least one occurrence of the symptom at Grade 2 or Grade 3 between Day X and Day Y
At least Grade 3	All subjects with at least one occurrence of the symptom at Grade 3 between Day X and Day Y

#### **10.1.2.4. Unsolicited adverse events**

Missing severity, relationship with study vaccine, and outcome of unsolicited adverse events will not be replaced and will appear as 'UNKNOWN' in all statistical output.

#### **10.1.3. Data derivation**

##### **10.1.3.1. Age at vaccination in years**

When age at vaccination is to be displayed in years, it will be calculated as the number of complete calendar years between the date of birth and the date of vaccination. For example:

DOB = 10SEP1983, Date of vaccination = 09SEP2018 -> Age = 34 years

DOB = 10SEP1983, Date of vaccination = 10SEP2018 -> Age = 35 years

##### **10.1.3.2. Body mass index (BMI)**

BMI will be calculated as follows:

$$\text{BMI} = (\text{weight in kilograms}) / (\text{height in meters})^2$$

**CONFIDENTIAL**209538 (NTHI MCAT-009)  
Statistical Analysis Plan Amendment 2**10.1.3.3. Numerical serology results**

Numerical serology results will be derived from the content of IS.ISORRES in the SDTM dataset. For assays with a specific cut-off, the following derivation rules apply:

IS.ISORRES	Derived value
“NEG”, “-“, or “(-)”	cut-off/2
“POS”, “+”, or “(+)”	cut-off
“< value” and value is <= assay cut-off	cut-off/2
“< value” and value is > assay cut-off	value
“> value” and value is < assay cut-off	cut-off/2
“> value” and value is >= assay cut-off	value
“value” and value is < cut-off	cut-off/2
“value” and value is >= cut-off	value
All other cases	missing

**10.1.3.4. Geometric mean concentrations (GMCs)**

GMC calculations are performed by taking the inverse logarithm of the mean of the log-10 concentration transformations. Antibody concentrations below the cut-off of the assay will be given an arbitrary value of half the cut-off of the assay for the purpose of GMC calculation. The cut-off value is defined by the laboratory before the analysis and is described in the protocol.

**10.1.3.5. Onset day**

The onset day for an event (e.g. AE, medication, vaccination) is the number of days between the last study vaccination and the start date of the event. This is 1 for an event occurring on the same day as a vaccination (and reported as starting after vaccination).

**10.1.3.6. Duration of events**

The duration of an event with a start and end date will be the number of days between the start and end dates plus 1 day, i.e. an event that starts on 03MAR2018 and ends on 12MAR2018 has a duration of 10 days.

The duration of solicited events will be calculated as the sum of the consecutive days with the symptom reported at Grade 1 or higher. The duration of solicited events at a specific grade (e.g. Grade 3) will be calculated as the sum of the consecutive days with the symptom reported at that grade. The same rule applies for solicited events ongoing at the end of the solicited follow-up period considering the maximum intensity reported.

**CONFIDENTIAL**

209538 (NTHI MCAT-009)  
 Statistical Analysis Plan Amendment 2

**10.1.3.7. Counting rules for combining solicited and unsolicited adverse events**

For output combining solicited and unsolicited adverse events, all serious adverse events will be considered general events since the administration site flag is not included in the expedited adverse event eCRF pages.

Multiple events with the same preferred term which start on the same day are counted as only one occurrence.

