**Table 1 Study groups, treatment and epochs foreseen in the study**

Study Groups	Number of subjects	Age (Min-Max)	Treatment name	Epochs (Blinding)	
				Epoch 001 (open-label)	Epoch 002 (open-label)
Sh_NTHi-Mcat_1	135	50 – 80 years	Shingrix / NTHi-Mcat	●	●
Sh_NTHi-Mcat_3	135	50 – 80 years	Shingrix / NTHi-Mcat	●	●
Sh_NTHi-Mcat_6	135	50 – 80 years	Shingrix / NTHi-Mcat	●	●
NTHi-Mcat	135	50 – 80 years	NTHi-Mcat	●	●

- **Treatment allocation:** Subjects will be allocated to a study group using an automated, electronic System Built for Internet Randomization (SBIR). The randomization algorithm will use a minimization procedure accounting for age category (50–59, 60–69, 70–80 years of age), smoking status (current or former smoker), and centre. Minimization factors will have equal weight in the minimization algorithm.
- **Blinding:** open-label.
- **Data collection:** Electronic Case Report Form (eCRF). Telephone contact. Solicited and unsolicited symptoms will be collected using a subject Diary (paper diary [pDiary]).
- **Safety monitoring:** Subjects will be observed for at least 60 minutes after each NTHi-Mcat vaccination for any immediate reactions. Solicited local and general AEs occurring during a 7-day follow-up period after each NTHi-Mcat vaccination (i.e. the day of vaccination and the 6 subsequent days) and unsolicited AEs occurring during a 30-day follow-up period after each NTHi-Mcat vaccination (i.e. the day of vaccination and the 29 subsequent days), will be reported via diary cards. In addition, subjects will be asked at Phone contacts if there were any safety concerns in the 7-day follow-up period after each NTHi-Mcat vaccination; this information will be recorded via the appropriate section of the eCRF. Finally, safety assessments will be performed during each clinic visit and safety follow-up calls to collect information on AEs leading to withdrawal, serious adverse events (SAEs), SAEs related to study participation or to a concurrent GSK medication/vaccine, pregnancies, potential immune-mediated diseases (pIMDs), throughout the whole study period.

**CONFIDENTIAL**209538 (NTHI MCAT-009)  
Statistical Analysis Plan Amendment 2**3. OBJECTIVES AND ENDPOINTS**

Objectives	Endpoints
Primary	

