Secondary	
Within group assessment
 
The percentage of subjects with at least 1 local adverse event (AE) (solicited and unsolicited), with at least 1 general AE (solicited and unsolicited) and with any AE during the 7-days solicited follow-up period and the 30-days follow-up period will be tabulated by group with exact 95% CI after each NTHi-Mcat vaccine dose and overall. The percentage of NTHi-Mcat doses followed by at least 1 local AE (solicited and unsolicited), by at least 1 general AE (solicited and unsolicited) and by any AE will be tabulated by group with exact 95% CI. The same calculations will be performed for AEs rated as Grade 3, for AEs causally related to vaccination and Grade 3 AEs causally related to vaccination.
 
The percentage of subjects reporting each individual solicited local and general AE during the 7-days solicited follow-up period after each dose of NTHi-Mcat vaccine will be tabulated by group with exact 95% CI. The percentage of NTHi-Mcat doses followed by each individual solicited local and general AE will be tabulated by group with exact 95% CI.
 
Fever will be reported per 0.5°C cumulative increments.
 
For all solicited symptoms, the same tabulation will be performed for Grade 3 AEs.
 
The verbatim reports of unsolicited symptoms will be reviewed by a physician and the signs and symptoms will be coded according to the Medical Dictionary for Regulatory Activities (MedDRA) Dictionary for Adverse Event Terminology. The percentage of subjects with at least 1 report of unsolicited adverse event classified by the MedDRA and reported up to 30 days after NTHi-Mcat vaccinations will be tabulated by group with exact 95% CI. The same tabulation will be performed for Grade 3 unsolicited adverse events, for unsolicited adverse events with a causal relationship to vaccination and for Grade 3 AEs causally related to vaccination.
 
The number of subjects who experienced any serious adverse event (SAE) or any potential immune-mediated disease (pIMD) from Day 1 to Day 331 and from Day 331 to Day 661 will be reported.
 
The number of subjects who experienced any AE leading to study withdrawal, from first vaccination up to study conclusion, or any SAE related to study participation or concurrent GSK medication/vaccination, during the entire study period, will be reported.
 
A summary of subjects reporting concomitant medication/product will be provided.

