#### **5.4.2.3. Combined analysis of solicited and unsolicited AEs**

The combined analysis of solicited and unsolicited AEs will be performed on the Unsolicited safety set.

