**CONFIDENTIAL**

209538 (NTHI MCAT-009)  
 Statistical Analysis Plan Amendment 2

Solicited AEs will be coded by MedDRA as per the following codes:

Solicited symptom	Preferred Term code	Corresponding Preferred Term decode
Pain	10022086	Injection site pain
Redness	10022061	Injection site erythema
Swelling	10053425	Injection site swelling
Headache	10019211	Headache
Fatigue	10016256	Fatigue
Gastrointestinal symptoms	10017944	Gastrointestinal disorder
Myalgia	10028411	Myalgia
Chills	10008531	Chills
Fever	10037660	Pyrexia

Combined analysis of solicited and unsolicited AEs will be also stratified on AEs with a causal relationship to NTHi-Mcat vaccination (all solicited AEs are considered causally related).

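### Counting every SAE as general in the combined AE tables can drop a serious injection-site reaction from the local rows

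*SAP*

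**What the plan says.** SAP Amendment 2, section 5.4.1, plans combined tables by group: "The percentage of subjects with at least 1 local adverse event (AE) (solicited and unsolicited), with at least 1 general AE (solicited and unsolicited"). A further row counts subjects who had an AE of either kind. These cover the 7-day and 30-day periods after each NTHi-Mcat dose and overall, and there is a parallel version per dose. The tables are then repeated: "The same calculations will be performed for AEs rated as Grade 3, for AEs causally related to vaccination", and for Grade 3 related events. Section 5.4.2.3 fixes the population: "The combined analysis of solicited and unsolicited AEs will be performed on the Unsolicited safety set".

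The local/general status of an SAE in this output is set by section 10.1.3.7: "all serious adverse events will be considered general events since the administration site flag is not included in the expedited adverse event eCRF pages". No other section restores local status to an SAE. The same section adds that events sharing a preferred term and a start day are one occurrence.

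Solicited symptoms have a separate route. SAP section 2 collects "Solicited local and general AEs occurring during a 7-day follow-up period after each NTHi-Mcat vaccination" on diary cards. SAP 10.1.2.3.1 takes local or general status from the diary question: "Denominators for the summary of local (or general) solicited symptoms will be calculated using the number of subjects who respond" either way to it. Protocol 12.5.3 limits the solicited local symptoms to pain, redness and swelling. Protocol 12.5.8.2.2 treats all solicited reactions as related.

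**The concern.** The rule follows from a gap in the form, not from the nature of the event. If a serious reaction at the injection site reaches the database only through the expedited report, the combined tables show it as a general event. It is then absent from the local row, from the related local row if the investigator judged it related, and from the Grade 3 local row if graded 3. The corresponding general rows gain it.

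Local tolerability is a natural question in this design. The three Sh groups are scheduled for two Shingrix and two NTHi-Mcat doses in the same arm, against two NTHi-Mcat doses in control (protocol 5.2 and Table 9). A reader looking at the local rows after NTHi-Mcat would expect a serious injection-site reaction to be there. Reactions to the Shingrix doses themselves are outside these tables under any wording, because the tables count events after NTHi-Mcat doses.

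The missing flag does not force the rule. Under SAP 5.4.1 unsolicited events are coded to MedDRA, and protocol 12.5.8.2.2 speaks of unsolicited AEs as including SAEs. The preferred term can therefore separate most injection-site events.

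**Working it through.** The plan gives no figure for this point, so there is nothing to reproduce. The check has two parts: which events are affected, and how far one of them moves a row.

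**Which events are affected**

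| Serious injection-site reaction | Diary record that counts it? | Effect of the rule |
|---|---|---|
| Pain, redness or swelling within 7 days, diary completed, same grade on both records | Yes: local and related, at the diary grade | Local rows keep the subject |
| Any other local reaction | No, only three local symptoms are solicited | Can be missing from local rows |
| Onset after the 7-day window, within 30 days | No; the protocol glossary makes it unsolicited | Can be missing from 30-day local rows |
| Solicited symptom, diary not completed | No | Can be missing from local rows |
| Graded 3 as an SAE but lower on the diary | Yes, but not at Grade 3 | Can be missing from Grade 3 local rows only |

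The last case can arise because diary redness and swelling reach Grade 3 only above 100 mm (SAP 5.4.2.1), while the investigator grades an SAE by clinical judgement (protocol 12.5.8.2.2).

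One situation is left open. If a diary record (local) and an SAE record (general) of the same reaction share a preferred term and start day, they count once, but the SAP does not say which status survives. If the start days differ, one reaction can count in both rows.

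**Size per affected subject**

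Inputs: 135 subjects per group (protocol 5.2), assumed all in the Unsolicited safety set; two NTHi-Mcat doses each, assumed all given; exact Clopper-Pearson 95% intervals (SAP 10.1.5.1).

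- Subject-level local row, no other local AE in that row: 1/135 = 0.74 percentage points. With another local AE in that row: 0.
- Dose-level row: 1/(2 × 135) = 1/270 = 0.37 points.
- Sparse row, such as Grade 3 local: 0/135 = 0% (0 to 2.70%) under the rule, against 1/135 = 0.74% (0.02 to 4.06%) if the event were counted as local.
- General row: the SAE adds 0.74 points only if the subject has no other general AE there. If a share g of subjects has one, the expected addition is (1 − g)/135. For assumed g of 30%, 50% and 70% this is 0.52, 0.37 and 0.22 points.
- Smaller set: with 108 subjects, used only as an illustration (the evaluable number in protocol 10.1.2), one event is 1/108 = 0.93 points.
- Any-AE row: 0, because the event counts there under either status.

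The documents give no rate of serious injection-site reactions, so a total effect cannot be computed.

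**The case against.** The rule is openly stated with its reason, sits among the sponsor's standard conventions (SAP 10.1), and applies identically to all four groups. SAEs are analysed separately on the Exposed Set, including fatal and related events by vaccine (SAP 5.4.2.4). Unsolicited events are tabulated by MedDRA term, and solicited local symptoms have their own tables. All of this stands, and it keeps the point small.

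Three stronger readings are tempting, and the documents do not support them.

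- *That every serious injection-site reaction is lost from the local rows.* Nothing removes a diary record because the same event is also an SAE. A subject with serious pain, redness or swelling recorded on a completed diary within 7 days has a local, related diary record.
- *That a serious local reaction is by definition a Grade 3 one.* Protocol 12.5.8.2.2 warns against confusing the two. A serious event leaves a gap in the Grade 3 local row only if it was also graded 3.
- *That 0.74 points is a ceiling.* The denominator is the Unsolicited safety set, which requires at least one NTHi-Mcat dose (SAP 4.1.1). If it has fewer than 135 subjects in a group, one event moves the row by more.

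The term-based remedy also has limits. SAP 5.4.2.3, which begins "Solicited AEs will be coded by MedDRA as per the following codes", assigns terms to symptoms already known to be local or general; it does not infer site from the term. Investigators are told to record the diagnosis where one can be made (protocol 12.5.8.2.1), so a serious local event coded to a diagnosis would not be found. Influenza and pneumococcal vaccines are permitted under conditions (protocol 6.2.2), so an injection-site term could belong to a non-study injection.

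**Conclusion.** The point holds in a conditional form. The combined tables can omit a serious injection-site reaction from a local row in the four situations set out above, and only when no other local AE already counts the subject in that row. They can add it to a general row when no other general AE does. One event is worth about 0.74 percentage points at subject level with 135 subjects in the set, and slightly more with fewer. Such events should be few; that is an expectation, not a figure in the documents.

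The solicited-only tables, the separate SAE analysis, the any-AE row and the primary objective do not change. The affected tables are descriptive secondary safety output, so this is an optional improvement.

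**What to change.** Replace the sentence in SAP 10.1.3.7 with:

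*SAEs whose MedDRA preferred term is an injection-site or vaccination-site reaction term, and which are not attributed to a non-study injection, are counted as local; all other SAEs are counted as general. A reaction recorded both on the diary and as an SAE is counted once, as local.*

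The second sentence settles the double-record case that the SAP leaves open. No new data are needed. The cost is a wording change, one coding look-up and a check of the narratives of the SAEs found. Serious local events coded only to a diagnosis would still be counted as general. If the sponsor prefers to keep its standard rule, the minimum is a footnote to the combined tables listing any serious injection-site reactions by group.
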